2. OBJECTIVES AND ENDPOINTS

Primary Objectives (Safety)	Primary Endpoints (Safety)

 To assess the effect of a single course of otelixizumab treatment on the acute and long term safety and tolerability of otelixizumab in NOT1DM patients. 	
 Incidence of adverse events (AEs) particularly those related to Cytokine release syndrome (CRS). Epstein-Barr virus (EBV) reactivation over Day 21 to Month 24. Changes in laboratory values, electrocardiograms (ECGs) and vital signs over Day 14 to Month 24.
Secondary Objectives (Pharmacokinetic)	Secondary Endpoints (Pharmacokinetic)

 To assess the pharmacokinetics of repeat dose administration of otelixizumab over 14 days in NOT1DM patients. 	
 Free serum otelixizumab concentrations over Days 1-14 and summary PK parameters.
Secondary Objectives (Efficacy)	Secondary Endpoints (Efficacy)

 To assess the effect of a single course of otelixizumab treatment on the rate of decline of pancreatic β-cell function over 24 months in NOT1DM patients. 	
 Change from baseline in C-peptide and glucose AUC (0-120) after a Mixed Meal Tolerance Test at Month 3, 6, 12, 18 and 24.

 To assess the effect of a single course of otelixizumab treatment on the rate of decline of C-peptide response and insulin sensitivity of β-cell function determined after a hyperglycemic clamp over 24 months in NOT1DM patients. 	
 Change from baseline in C-Peptide and glucose AUC hyperglycemic phase [H60 to H140 minutes] and insulin sensitivity (IS) index after a hyperglycemic clamp at Months 6 and 24.

 To assess the effect of a single course of otelixizumab treatment on exogenous insulin use for otelixizumab over 24 months in NOT1DM patients. 	
 Change from baseline in mean daily insulin use over 7 consecutive days during the week preceding all visits and phone calls.

 To assess the effect of a single course of otelixizumab treatment on glycaemic control over 24 months in NOT1DM patients. 	
 Change from baseline in HbA1c level. Body weight Day -1, Months 12-24. Hypoglycemic and hyperglycemic events over Months 1-24.

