3.3.1.2. Study Duration

Data from the literature at the origin of the study design identified a causal relationship between the degree of immunosuppression and an increased incidence of EBV related Post Transplant Lymphoproliferative Disorders (PTLD) and for this reason a long-term follow-up (60 months) was implemented at the start of the study. The interim analysis data which emerged from this study showed a prompt regain of immune competence observed in treated subjects and consequent rapid resolution of EBV reactivation, both clinically and virologically. The long term EBV related PTLTD risk, as observed in solid organ transplant on a chronic immune suppression therapy, is negligible. As a result, the overall study duration for each subject will be 24 months, except for those patients who have already passed the 24 month or 36 month follow up, in which case they will have a final follow up communication (telephone call or visit) as soon as possible following approval of this amendment 08 of the protocol. Further details are provided in the Study Reference Manual (SRM). If further follow up is required, the Investigator will request that the patient visits the site. See Section 9.3 for a description of analysis considerations.

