
Epstein-Barr virus (EBV)
	
 • Epstein-Barr virus (EBV) is a widespread human gamma herpes-virus. • Primary infection with EBV usually occurs asymptotically, where after the virus persists for life in a latent form in B lymphocytes. • The initial expansion and reactivation of these latently infected B lymphocytes is controlled by specific CD8+ major cytotoxic T-lymphocyte (CTL) responses. • EBV reactivation is accompanied by one or more of the following: rash; elevated liver function tests, other signs and symptoms consistent with acute infectious mononucleosis (pharyngo-laryngeal pain, acute tonsillitis, lymphadenopathy, fever). • The most sensitive confirmation of EBV reactivation is by detecting an increase in viral copy number (by RT-PCR). • In patients on chronic immune-suppression persisting EBV reactivation can be detected. Chronic EBV reactivation is thought to be causal for early post-transplant lymphoproliferative disorder (PTLD) which may occur in up to 30-40% of patients chronically maintained on high dose immunosuppression. • In studies with otelexizumab in patients with NOT1DM an increased incidence of transient EBV reactivation with regimens employing higher daily doses has been observed (i.e. 48-64mg cumulative tested in the BDR study). Rapid immune response was evident and full immunity to EBV was restored with no evidence of recurring viremia. Maximum EBV levels occurred around Week 3 and decreased to baseline around Month 3. • As daily dose increases, so the degree of lymphopenia increases and TCR/CD3 surface expression declines, resulting in approximately 90% reduction in surface expression of TCR/CD3 of 90% sustained. 	
Patients within 3 months of evidence of acute/active EBV infection (e.g)
 
 • Symptomatic • Positive EBV capsid Ab IgM in absence of a positive EBV EBNA Ab IgG • EBV viral load of >10,000 copies per 10⁶ lymphocytes 
will not be enrolled in the study.
	
 • Patients with previous history of immunosuppression and/or on active immunosuppressant therapy will be excluded from this study • Patients will be monitored for clinical symptoms of mononucleosis and changes in EBV viral load.

Potential Risk	Summary of Data	Impact- Eligibility Criteria	Strategy-Monitoring/Stopping Criteria

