5.3.2. EBV Stopping Criteria

Three parameters as described in [Table 7](#) will be used to assess EBV reactivation at a patient level to determine dose escalation:

Table 7 Parameters used to Assess EBV Reactivation

Parameter	Criteria
Clinical Symptoms of Mononucleosis	Fever, fatigue, malaise, myalgia, pharyngodynia, lymphadenopathy
Change in Viral Load	EBV by PCR more than 10,000 copies per 10 ⁶ peripheral blood mononuclear cells
Change in Serology	Emergence of IgM for EBV on otherwise EBV-IgG positive patients

Table 8 shows the possible combinations of the three EBV parameters that will be used to assess whether the patient has clinical EBV reactivation for the purpose of the stopping criteria. The assessment will be conducted for each subject at approximately 6 weeks post first active dose.

Table 8 Assessment of EBV Reactivation

Clinical Signs of Mononucleosis	Serology	Virology	EBV Reactivation
+	-	-	NO*
+	+	+	YES
+	+	-	YES
+	-	+	YES
-	-	-	NO
-	+	+	NO
-	+	-	NO
-	-	+	NO

*Other causes of mononucleosis should be checked

There will be ongoing reviews of safety data throughout the trial progression and on completion of each cohort.

[figure not shown]
If $\geq 3/8$ patients on active treatment within a cohort develop symptoms of clinical EBV reactivation as described above, the dosing will be stopped and no further dosing will be carried out on any other patients; patients who have been dosed will be followed up as per protocol.

Patient history will be assessed for symptoms of infectious mononucleosis, and spontaneous AE reporting will be implemented for assessing clinical EBV reactivation.

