9.3.3. Safety Analyses

Safety data will be presented in tabular and/or graphical format and summarized descriptively according to GSK's Integrated Data Standards Library (IDSL) standards.

Further details, regarding specific analyses of safety endpoints (e.g. Cytokine Release Syndrome and Epstein-Barr Virus) will be further detailed and included in the RAP.

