11.10.5. Safety Tables

Safety: Tables					
No.	Population	IDSL / TST ID / Example Shell	Title	Programming Notes	Deliverable [Priority]
AE					
2.01.	Safety	AE13	Adverse Event Overview	Split as described in Section 11.3	FA (SAC)
2.02.	Safety	AE15	Summary of All Adverse Events by System Organ Class and Preferred Term	Split as described in Section 11.3 Add a "Any Event" category for each SOC even if not in shell	FA (SAC)
2.03.	Safety	AE15	Summary of Drug-Related Adverse Events	Split as described in Section 11.3 Add a "Any Event" category for each SOC even if not in shell	FA (SAC)
2.04.	Safety	AE16	Summary of Serious Adverse Events by System Organ Class and Preferred Term	Split as described in Section 11.3	FA (SAC)
2.05.	Safety	AE1	Summary of AEs Leading to Permanent Discontinuation of Study Drug or Withdrawal from Study	Do not split this output by phase	FA (SAC)
2.06.	Safety	AE5	Summary of All Adverse Events by Maximum Grade by System Organ Class and Preferred Term	Split as described in Section 11.3	FA (SAC)
2.07.	Safety	AE5	Summary of Drug-Related Adverse Events by Maximum Grade by System Organ Class and Preferred Term	Split as described in Section 11.3	FA (SAC)
Cytokine Release Syndrome					

2.08.	Safety	AE15	Summary of Adverse Events - Cytokine Release Syndrome Induced Symptoms	
 • Definition of Cytokine Release Syndrome in Section 11.5.3 • Overall only, not split by study phase. 	FA (SAC)
Epstein-Barr Virus					
2.09.	Safety	AE15	Summary of Adverse Events Considered to be Potentially Associated with EBV Reactivation	
 • Clinical Symptoms of Mononucleosis AE Terms to include are in Section 11.5.3 • Overall only not split by study phase. 	FA (SAC)
2.10.	Safety	Non-Standard SAFE_T3	Summary of categorical values of Epstein-Barr Virus (Serology: IgG & IgM)	
 • Categories (negative, positive) to be derived from absolute values according to a worst case approach as described in Section 11.5.3 	FA (SAC)
2.11.	Safety	Non-Standard SAFE_T2	Summary of Epstein-Barr Viral Load (PCR)	
 • Geometric Means 	FA (SAC)
2.12.	Safety	Non-Standard SAFE_T4	Categorical Summary of Epstein-Barr Viral Load (PCR)		FA (SAC)

Labs

2.13.	Safety	LB1	Summary of Laboratory Values	
 Order parameters alphabetically. BY Labtype (1. Chemistry, 2. Haematology) 	FA (SAC)

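### EBV reactivation from Day 21 to Month 24 is a primary endpoint, but no SAP display counts, by dose, the patients who had it

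*SAP*

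**What the plan says.** Protocol Section 2 lists "Epstein-Barr virus (EBV) reactivation over Day 21 to Month 24" among the primary safety endpoints, and SAP 2.2 repeats it. On analysis, protocol 9.3.3 says: "Further details, regarding specific analyses of safety endpoints (e.g. Cytokine Release Syndrome and Epstein-Barr Virus) will be further detailed and included in the RAP".

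The only patient-level rule is in protocol 5.3.2. Table 7 names three parameters: symptoms of mononucleosis, more than 10,000 copies per 10^6 PBMC, and emergent IgM in an IgG-positive patient. Table 8 combines them into YES or NO, and is stated to be "for the purpose of the stopping criteria. The assessment will be conducted for each subject at approximately 6 weeks post first active dose".

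SAP 11.5.3 derives the three parts separately: six symptom preferred terms, positive or negative serology, and viral load categories. The symptom terms feed Table 2.09, "Summary of Adverse Events Considered to be Potentially Associated with EBV Reactivation". Its programming note gives the same instruction as the one for CRS Table 2.08: "Overall only, not split by study phase". Serology goes to Table 2.10 and viral load to Tables 2.11 and 2.12, all by visit. Listings 22 and 23 hold the AEs and the laboratory results.

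**The concern.** A primary endpoint should yield a number of patients with the event, out of those treated, for each dose. These displays do not yield one, so it would have to be built from listings by someone who has already seen them and who must choose a definition on the way. The choice is open, because protocol 3.4 calls a rise in viral copy number the most sensitive confirmation, whereas Table 8 requires symptoms as well.

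Table 2.09 is the display that a reader is most likely to take for the answer, and it differs from the endpoint in period and content. The protocol says of earlier experience that "Maximum EBV levels occurred around Week 3 and decreased to baseline around Month 3", which fits a window opening at Day 21. Table 2.09 starts with the infusions instead.

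**Working it through.** **1. What each display counts**

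| Display | Content | Period | Patient count over the window? |
|---|---|---|---|
| Table 2.09 | six symptom terms | whole study | symptoms only, no Day 21 start |
| Table 2.10 | IgG and IgM status, with shift from baseline | each visit | no |
| Table 2.11, Figure 2.02 | geometric mean viral load | each visit | no |
| Table 2.12 | viral load category, n (%) | each visit | no |
| Listings 22 and 23 | AEs; serology and PCR results | all | by hand only |

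SAP 11.4.3 keeps unscheduled visits out of summary tables and figures. A PCR or IgM result from an unscheduled visit therefore appears only in a listing.

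**2. Components against protocol Table 7.** The six SAP terms (pyrexia, fatigue, malaise, myalgia, oropharyngeal pain, lymphadenopathy) match the six Table 7 symptoms one to one. The load categories break at 10,000, the Table 7 cut-off. The negative-to-positive column of Table 2.10 shows emergent IgM. The parts are right; what is missing is the per-patient step.

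**3. Overlap with CRS.** Protocol 5.3.1 lists fever and myalgia among the CRS endpoints. The SAP's verbatim examples under pyrexia include shivering, which protocol Table 5 uses to describe Grade 1 chills.

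**4. Table 8 patterns** (order: symptoms, serology, virology).
- YES: +++, ++-, +-+ (3 of 8).
- Symptom-positive: these three plus +-- (4 of 8). Counting symptoms alone disagrees with Table 8 on 1 of 8.
- PCR-positive: +++, +-+, -++, --+. PCR alone disagrees with Table 8 on ++-, -++ and --+ (3 of 8).

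These count patterns, not patients. The documents give no pattern frequencies.

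**5. Reproducing protocol Table 10.** With a Beta(1,1) prior, x events in 8 give Beta(1+x, 9-x).
- x = 3: Beta(4,6), 95% interval 0.137 to 0.701 (printed 0.14, 0.70).
- x = 2: Beta(3,7), 0.075 to 0.600 (printed 0.07, 0.60).
- x = 4: Beta(5,5), 0.212 to 0.788 (printed 0.21, 0.79).
- x = 6: Beta(7,3), 0.400 to 0.925 (printed 0.40, 0.93).

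**6. What by-visit counts can say** (invented counts). If a of 8 are positive at one visit and b of 8 at another, the number ever positive lies between max(a, b) and min(8, a+b). With 2 at Day 21 and 2 at Week 6, that is 2 to 4 patients. The interval is then either 0.07 to 0.60 or 0.21 to 0.79.

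**7. What Table 2.09 can say** (invented counts). If 6 of 8 had a listed symptom but 2 of 8 met Table 8, Table 2.09 would suggest 0.40 to 0.93 where the joint count gives 0.07 to 0.60.

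**8. Would a phase split be enough?** The SAP 11.3 dosing phase ends the day after the last dose. With the last dose on Day 6, the next phase runs from Day 8 to the later of the Week 6 visit or Day 42. Day 21 falls inside it, so the phases alone do not isolate the endpoint window.

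**The case against.** The best defence is that the SAP follows protocol Table 7 part by part and reports both laboratory parts as subject n (%) by dose and visit. Table 2.09 claims only a potential association. Tables 2.02 and 2.06 show every AE term by phase. With 8 patients planned per dose, the two listings can be linked in minutes, and the study tests no formal hypothesis. All of this is correct. It rules out the reading that the SAP reports no EBV data by dose.

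A reader might also infer that Table 8 is the endpoint definition and that the SAP departs from it. The documents do not support that: Table 8 serves the stopping rule at about 6 weeks, and neither document adopts it for 24 months.

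The defence does not supply a count. A listing is not a planned result, and by-visit tables only bound the number ever positive. The SAP already plans worst-case or maximum post-baseline tables for laboratory values, QTc and vital signs (2.15, 2.18, 2.19, 2.21). It also plans patient-level responder tables for C-peptide and glycaemic response (3.16, 3.17), neither of which is a primary endpoint.

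The six-term list has two further gaps. It stays open until reporting. It also names no EBV or mononucleosis diagnosis, although protocol Appendix 4 has a diagnosis recorded in place of its symptoms.

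**Conclusion.** The point holds in a limited form and should be fixed. No display gives, by dose, the number of patients ever positive by IgM or PCR in the window, or the number with symptoms plus either. Followed as written, Table 2.09 puts dosing-period pyrexia and myalgia, and symptom-only patients, under an EBV title and outside the endpoint window.

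The effect on the reported rate cannot be computed, because the documents hold no results. The illustrations assume the planned 8 per dose; Cohort 3 may be smaller because stopping criteria were met there. I make no comparison with the 0.375 rate of protocol Table 10. The matching 3-of-8 rule concerns clinical reactivation, so it should not be applied to PCR positivity alone.

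Two stronger inferences are not supported. First, no pending dosing decision is at risk: SAP 2.3 says that escalation stopped in Cohort 3, and interim reviews fall under a separate RAP that is not among these documents and may hold such a count. Second, the cut in follow-up from 60 to 24 months did not rest on the missing table. Protocol 3.3.1.2 bases it on interim data showing "rapid resolution of EBV reactivation, both clinically and virologically", and the final displays could not have informed it. They should still let a reader see how many patients reactivated.

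**What to change.** 1. In SAP 11.5.3, state before database lock what the endpoint means, and derive patient-level flags. At about 6 weeks, use the protocol Table 7 and 8 status as written, and say that it is adopted from the stopping rule. For Day 21 to Month 24, derive: ever above 10,000 copies; ever-emergent IgM; and the Table 8 combination, using symptom AEs present in that window. Include unscheduled samples.

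2. Add one table of n/N (%) for each flag, by dose and pooled placebo, with the Beta(1,1) 95% credible interval already used in protocol Table 10. Footnote that the joint count requires no closeness in time between symptom and laboratory result, and so may overcount over 24 months.

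3. Split Table 2.09 by the SAP 11.3 phases and add a column for onset from Day 21 to Month 24. Add EBV and mononucleosis diagnosis terms, and close the list before lock. If wanted, a sensitivity count can leave out pyrexia and myalgia starting within the SAP's 14-day CRS window. The other four terms do not overlap with the CRS endpoints and should stay.

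The cost is a little programming on data already collected. The flags would be adopted after interim EBV results were known, and the SAP should say so.

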5.3. Patient Specific and Dose Escalation Stopping Criteria

5.3.1. Cytokine Release Syndrome Stopping Criteria

Cytokine Release Syndrome (CRS) experienced during the 6 days of dosing will be monitored specifically by the investigator according to the grading system presented in [Table 5](#) and Section 7.1.5. In-stream real time data review will be utilised, so as to limit patient exposure unnecessarily, if stopping criteria are met.

Table 5 CRS AE Grading System

Adverse Event	Grade 1	Grade 2	Grade 3	Grade 4	Grade 5
Headache	Mild pain	Moderate pain; limiting instrumental ADL	Severe pain; limiting self care ADL	-	-
Fever	38.0 - 39.0 degrees C	>39.0 - 40.0 degrees C	>40.0 degrees C for <=24 hrs	>40.0 degrees C for >24 hrs	Death
Vomiting	1 - 2 episodes (separated by 5 minutes) in 24 hrs	3 - 5 episodes (separated by 5 minutes) in 24 hrs	>=6 episodes (separated by 5 minutes) in 24 hrs	Life-threatening consequences; urgent intervention indicated	Death
Diarrhoea	Increase of <4 stools per day over baseline.	Increase of 4 - 6 stools per day over baseline.	Increase of >=7 stools per day over baseline; incontinence; limiting self care ADL	Life-threatening consequences; urgent intervention indicated	Death
Hypotension	Asymptomatic, intervention not indicated	Non-urgent medical intervention indicated	Urgent medical intervention indicated	Life-threatening and urgent intervention indicated	Death
Chills	Mild sensation of cold; shivering; chattering of teeth	Moderate tremor of the entire body; narcotics indicated	Severe or prolonged, not responsive to narcotics	-	-
Nausea	Loss of appetite without alteration in eating habits	Oral intake decreased without significant weight loss, dehydration or malnutrition	Inadequate oral caloric or fluid intake.	-	-

Adverse Event	Grade 1	Grade 2	Grade 3	Grade 4	Grade 5
Arthralgia	Mild pain	Moderate pain; limiting instrumental ADL	Severe pain; limiting self care ADL	-	-
Myalgia	Mild pain	Moderate pain; limiting instrumental ADL	Severe pain; limiting self care ADL	-	-

ADL= Activities of daily living

Pre-specified CRS individual patient and study dosing stopping criteria are presented in [Table 6](#) and should be followed by the Investigator.

- If individual patient criteria are met: Treatment for that patient will be stopped immediately, will not be restarted, and the patient will be followed up as per protocol.

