- If study dosing stopping criteria are met: In addition to the individual patient instruction above, no further patients will be dosed within the cohort currently being investigated and no further dose escalation will occur; patients who have been dosed will be followed up as per protocol.

The symptoms in [Table 6](#) have been classified as objective and subjective endpoints as follows:

Objective Endpoints: Fever, Diarrhoea, Vomiting, Hypotension

Subjective Endpoints: Headache, Chills, Nausea, Arthralgia, Myalgia

Based on the above classification four possible outcomes have been defined where dosing would be stopped, as described in [Table 6](#):

Table 6 Stopping Criteria for CRS-Adverse Events

Scenario	NCI-CTC Scores	Individual Subject Criteria
I	2 objective endpoints \geq grade 2 OR Fever, vomiting, or diarrhoea \geq grade 2 persisting >48 hours despite treatment	Stop treatment
II	1 objective endpoint \geq grade 2 AND 
 • 2 subjective endpoints (except chills) \geq grade 3 OR • 1 subjective endpoint \geq grade 3 and Chills \geq grade 2 	Stop treatment
III	Three subjective endpoints \geq grade 3 (except if one subjective endpoint is Chills, which only needs to be \geq grade 2)	Stop treatment
IV	1 objective endpoint \geq grade 4	Stop treatment
Study Dosing Stopping Criteria: 
 • If ≥ 3 subjects on otelixizumab treatment within a cohort meet individual Stopping Criteria I-III detailed above. 
Or
 
 • If 1 subject on otelixizumab treatment within a cohort meet individual Stopping Criteria IV. 		

Note: in order to meet individual stopping criteria, the reported objective or subjective endpoints must be of different types during one 24 hour dosing period for any of the scenarios involving more than one endpoint.

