#Patients will record insulin usage for 7 days prior to out-patient visits (up to Month 24) and before telephone call/visit in Month 36 (if applicable) or final follow up. Significant AEs including hypoglycaemic (≤3.9 mmol/L; ≤70 mg dL) and hyperglycaemic (>13.9 mmol/L; >250 mg/dL) events will be recorded in a diary whenever they occur, to include start and stop dates.

1. Patient admitted evening of Day -2
2. Discharged on Day 6 if health considered satisfactory by the investigator. Dosing Day 4-6 may be performed on out-patient basis (see Section 3.1)
3. Physical exam performed to monitor for changes in clinical status
4. ECG pre-dose (in triplicate), at the end of the infusion and 6 hours post start infusion (if infusion <6 hours)
5. Vital signs include temperature, blood pressure and pulse rate (in triplicate), and respiration rate
6. See Section 6.2.3 for timings
7. Pre-dose on dosing days
8. If LFTs have shown an upward trend continue to monitor daily after day 6
9. HSV-1 & HSV-2 IgG & IgM will be measured at Day -1 and during the study if clinically indicated
10. If still positive at 6 months EBV viral load will be monitored every 3 months until month 24
11. One sample during visit
12. Blood samples for C-peptide and glucose levels collected at -10, 0, 15, 30, 60, 90 and 120 minutes
13. Plasma C-peptide and glucose levels will be measured during the hyperglycaemic clamp procedure at the following time points: L150, L165 and L180 minutes [during the euglycaemic (L)ow phase], H0, H60, H90, H120 and H140 minutes [during the hyperglycaemic (H)igh phase]
14. Mixed Meal and Glucose Clamp must be separated by at least 4 days
15. Patients will be asked to report verbally their HbA1c at Month 36 (if applicable) and/or final follow-up; followed eventually (if available) by a printed result via regular mail (or scan electronically).
16. Limited biomarkers on Day 6 pre-dose
17. Blood samples for exploratory biomarkers will only be analysed at Month 24 if indicated based on Month 12 results
18. One PGx (DNA) saliva sample taken between Day 1 and 6

6.2.3. Detail for Vitals, ECG and Pharmacokinetic and Pharmacodynamic Monitoring over the Infusion Period (Cohorts 1-4)

Day	Cohort	Assessment	Pre Dose	0 H	30 M	1 H	2 H	3 H	4 H	5 H	6 H	7 H	8 H	9 H	10 H	11 H	12 H	13 H	14 H	15 H	16 H			
1	C1	Dosing																						
		Vitals ^{1,2}	X	X		X	X	X	X	X	X	X	X	X	X	X	X	X	X				X	
		ECG	X									X			X									
		PK/CD3 Saturation	X		X	X	X		X		X		X	X									X	

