	C2-C4	Dosing																						
		Vitals ^{1,2}	X	X		X	X	X	X	X	X	X	X	X	X	X	X	X	X	X	X	X	X	
		ECG	X									X						X						
PK/CD3 Saturation	X		X	X	X		X		X		X		X			X					X			
2	C1-C4	Dosing																						
		Vitals ^{1,2}	X	X		X	X	X	X	X	X	X	X	X	X	X		X					X	
		ECG	X									X												
		PK/CD3 Saturation	X																					
3	C1-C4	Dosing																						
		Vitals ^{1,2}	X	X		X	X	X	X	X	X	X	X	X				X					X	
		ECG	X						X			X												
		PK/CD3 Saturation	X																					

Day	Cohort	Assessment	Pre Dose	0 H	30 M	1 H	2 H	3 H	4 H	5 H	6 H	7 H	8 H	9 H	10 H	11 H	12 H	13 H	14 H	15 H	16 H	
4	C1-C4	Dosing																				
		Vitals ^{1,2}	X	X		X	X	X ³														
		ECG	X			X		X ³														
		PK/CD3 Saturation	X																			
5	C1-C4	Dosing																				
		Vitals ^{1,2}	X	X		X	X	X ³														
		ECG	X			X		X ³														
		PK/CD3 Saturation	X																			
6	C1-C4	Dosing																				
		Vitals ^{1,2}	X	X		X	X	X ³														
		ECG	X			X		X ³														
		PK/CD3 Saturation	X			X																

1. Blood pressure to be taken in triplicate at Pre-dose
2. Vitals to be repeated at 30 min intervals should there be any safety concern
3. If patients are dosed on an out-patient basis on Day 4, 5 and 6, vital signs and ECGs will stop after the 3 hour post dose time point (if the Investigator is satisfied with the clinical status of the patient), if there are any concerns then vital signs and ECGs may be continued as judged necessary by the investigator until the investigator is satisfied

Day	Cohort	Assessment	Preferably within first hour of visit, time to be recorded in eCRF
14	C1-C4	PK/CD3 Saturation	X

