6.4.2. Vital Signs

Vital sign measurements will be measured in a semi-supine position after 5 minutes rest (before the first measurement) and will include systolic and diastolic blood pressure and pulse rate (triplicate measures, the average will be recorded in the eCRF), respiratory rate and temperature.

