11.7.3. Vital Signs

Vital Sign Parameter (Absolute)	Units	Clinical Concern Range	
		Lower	Upper
Systolic Blood Pressure	mmHg	< 85	> 160
Diastolic Blood Pressure	mmHg	< 45	> 100
Heart Rate	bpm	< 40	> 110
Respiration Rate	Min ⁻¹	< 10	> 30

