2.14.	Safety	LB1	Summary of Laboratory Changes from Baseline	
 Order parameters alphabetically BY Labtype (1. Chemistry, 2. Haematology) 	FA (SAC)
2.15.	Safety	LB15	Summary of Worst Case Laboratory Results Relative to Normal Range Post-Baseline Relative to Baseline	
 Order parameters alphabetically BY Labtype (1. Chemistry, 2. Haematology) 	FA (SAC)
Electrocardiograms					
2.16.	Safety	EG1	Summary of ECG Findings		FA (SAC)
2.17.	Safety	EG2	Summary of Change from Baseline in ECG Values		FA (SAC)
2.18.	Safety	EG10	Summary of Maximum QTc Values Post-Baseline Relative to Baseline by Category		FA (SAC)
2.19.	Safety	EG11	Summary of Maximum Increase in QTc Values Post-Baseline Relative to Baseline by Category		FA (SAC)
Vital Signs					
2.20.	Safety	VS1	Summary of Change from Baseline in Vital Signs		FA (SAC)
2.21.	Safety	VS7	Summary of Worst Case Vital Sign Results Relative to Potential Clinical Importance (PCI) Criteria Post-Baseline Relative to Baseline		FA (SAC)

Immunogenicity					
2.22.	Safety	Non-Standard EFF_T4	Summary of Immunogenicity	
 With positive instead of responder 	FA (SAC)

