22.	Safety	AE8	Listing of All Adverse Events – Considered Potentially Associated with EBV Reactivation	
 See Section 11.5.3 for definition 	FA (SAC)
23.	Safety	OTHER_L12	Listing of Epstein-Barr Virus Serology: IgG & IgM and Viral Load: PCR	Please include the following: EBCIGGAS, EBVMSOS, EBCIGGAB, EBVMABZ, EBCIGMAB, EBVDNA	FA (SAC)
LABS					
24.	Safety	LB5	Listing of All Haematology Laboratory Data for Subjects with Abnormalities of Potential Clinical Importance		FA (SAC)
25.	Safety	LB14	Listing of Haematology Laboratory Data with Character Results		FA (SAC)
26.	Safety	LB5	Listing of All Clinical Chemistry Laboratory Data for Subjects with Abnormalities of Potential Clinical Importance		FA (SAC)
27.	Safety	LB14	Listing of Clinical Chemistry Laboratory Data with Character Results		FA (SAC)
28.	Safety	LB5	Listing of All Serology Data		FA (SAC)
29.	Safety	LB14	Listing of Serology Data with Character Results		FA (SAC)
ECG's					
30.	Safety	EG3	Listing of ECG Values of Potential Clinical Importance		FA (SAC)
31.	Safety	EG3	Listing of All ECG Values for Subjects with Any Value of Potential Clinical Importance	Including change from Baseline	FA (SAC)

ICH : Listings					
No.	Population	IDSL / TST ID / Example Shell	Title	Programming Notes	Deliverable [Priority]
32.	Safety	EG5	Listing of Abnormal ECG Findings		FA (SAC)
Vital Signs					
33.	Safety	VS4	Listing of Vital Signs of Potential Clinical Importance		FA (SAC)
34.	Safety	VS4	Listing of All Vital Signs for Subjects with Values of Potential Clinical Importance		FA (SAC)
Pharmacokinetics					
35.	Safety	PK07	Listing of free serum concentration-Time Data		FA (SAC)

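### SAP 11.7.3 sets a concern range for every collected vital sign except temperature, so no planned display counts patients by measured fever and dose

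*SAP*

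**What the plan says.** The protocol treats temperature as a vital sign. Section 6.2.2, footnote 5, reads "Vital signs include temperature, blood pressure and pulse rate (in triplicate), and respiration rate", and Section 6.4.2 includes temperature in each set of measurements. Section 6.2.3 schedules vital signs before dosing, at the start of infusion and repeatedly afterwards on each of Days 1 to 6, with the instruction "Vitals to be repeated at 30 min intervals should there be any safety concern".

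Section 5.3.1 splits the CRS symptoms into two groups, the first being "Objective Endpoints: Fever, Diarrhoea, Vomiting, Hypotension". Table 5 grades fever by the temperature itself: grade 1 is "38.0 - 39.0 degrees C", grade 2 is above 39.0 and up to 40.0, and grades 3 and 4 are above 40.0, separated by whether it lasts more than 24 hours.

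SAP 11.7.3 lists absolute limits for four parameters: systolic pressure (below 85, above 160), diastolic pressure (below 45, above 100), heart rate (below 40, above 110) and respiration rate (below 10, above 30). Temperature has no row. Table 2.21 is titled "Summary of Worst Case Vital Sign Results Relative to Potential Clinical Importance (PCI) Criteria Post-Baseline Relative to Baseline". Listing 33 prints the individual values of potential clinical importance, and Listing 34 is the "Listing of All Vital Signs for Subjects with Values of Potential Clinical Importance".

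**The concern.** Adverse events, particularly those related to CRS, lead the primary safety endpoints. Of the nine symptoms in protocol Table 5, fever is the only one graded purely by an instrument reading. Even hypotension is graded by the intervention it needs. Under SAP 11.5.3, sponsor medical review decides which events count as CRS. Protocol 5.4 says that site, CRO and sponsor staff are all unblinded, although it also restricts the randomisation code to the pharmacist. The recorded temperatures are therefore the natural independent check on whether event-based fever and CRS counts by dose are complete.

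The SAP gives other objective safety measures that treatment. Viral load has a categorical table with a break at 10,000 copies, the same threshold as protocol Table 7. QTc has category tables. Low blood pressure has a concern range. Temperature has no equivalent.

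**Working it through.** No sample-size figure is involved. The check compares what is collected with what is classified, then follows each display that could carry fever.

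**Step 1: collected against classified**

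| Parameter | Collected (protocol 6.2.2, 6.4.2) | Range in SAP 11.7.3 |
|---|---|---|
| Systolic pressure | yes | yes |
| Diastolic pressure | yes | yes |
| Heart rate / pulse | yes | yes |
| Respiration rate | yes | yes |
| Temperature | yes | none |

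Four of five have a range, and the missing one defines a CRS grade.

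**Step 2: vital-sign displays**

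- Table 2.21 classifies the worst post-baseline value against the 11.7.3 limits. With no temperature limit, it has nothing to classify temperature against.
- Listing 33 prints only values outside a limit, so a temperature cannot appear in it.
- Listing 34 selects patients by the same limits, then prints all their vital signs. A febrile patient with, say, a heart rate above 110 appears with temperatures shown. A patient whose only abnormality is fever does not.
- Table 2.20 summarises change from baseline. It does not use the limits and excludes no parameter, so temperature is in scope. It describes a dose group at each time point and does not count febrile patients.

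**Step 3: adverse-event displays**

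- Tables 2.02 and 2.06 cover all adverse events by preferred term, split by study phase; Table 2.06 adds maximum grade. Reported pyrexia appears here with no CRS selection.
- Table 2.09 extracts pyrexia by preferred term as a possible symptom of mononucleosis.
- Table 2.08 and Listing 21 depend on CRS selection by expert review.
- All of these start from a reported event. Protocol Appendix 4 also asks that, where a diagnosis is established, the diagnosis be recorded in place of its signs, so a fever could in principle sit under another term.

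**Step 4: what a time-point mean does with a short fever**

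Assume one patient in a dose group of 8 rises 1.5 to 2.0 degrees C at a given time point and the other seven do not change. The group mean change is then 1.5/8 = 0.19 to 2.0/8 = 0.25 degrees C. If three patients peak at three different time points, the mean moves by that amount three times, and no figure in a mean column says that three patients were febrile. A maximum column, if the table has one, would show each peak but still not how many patients it came from.

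**Step 5: repeat readings**

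The protocol's extra 30-minute readings are triggered by concern, so they are the ones most likely to catch a fever. SAP 11.4.3 uses planned times in summaries, keeps unscheduled visits out of tables and sends unplanned readings to listings. For fever-only patients, the vital-sign listings are the ones that step 2 shows to be incomplete.

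**The case against.** The strongest reply is that fever is already reported. Protocol 7.1.5 has CRS events during dosing graded against Table 5, where the fever grade follows from the measured temperature. Table 2.06 gives events by maximum grade, dose and phase, including a dosing phase. A fever that was reported and graded is therefore counted per patient in nearly the bands proposed here. This stands, and it narrows the gap to fevers that were measured but not reported, or were recorded under another term. The documents give no sign of how many to expect.

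It is also fair that no stopping decision waits on these outputs. CRS stopping used real-time review, and SAP 2.3 records that escalation had already stopped in Cohort 3. SAP 7.6 defers to sponsor display standards unless otherwise specified, and those may hold a default temperature range. They are not in the documents, and 11.7.3 is the SAP's own list.

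Four stronger readings are tempting and should not be drawn:

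- A reader might infer that the vital-sign listings can never show fever. Listing 34 shows it for anyone flagged on another parameter.
- A reader might infer that fever surfaces only when selected as CRS. Tables 2.02, 2.06 and 2.09 need no such selection.
- A reader might infer that Table 2.20 would look flat. Its layout is not in the documents, and the SAP's own continuous shells print minimum, median and maximum, so an individual peak may well be visible.
- A reader might equate 3 of 8 febrile patients with the stopping proportion. The rule counts patients who meet a Table 6 scenario. From an assumed baseline of 37.0 degrees C, a rise of 1.5 to 2.0 gives 38.5 to 39.0, which is grade 1, and every Table 6 scenario that uses an objective endpoint needs at least grade 2.

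**Conclusion.** The point holds as a narrow reporting gap. Temperature is the one collected vital sign without a concern range, so Table 2.21 and Listing 33 cannot flag fever, and Listing 34 omits patients whose only abnormality is fever. Reported fever is well covered. Measured fever is not counted by patient and dose anywhere in the planned displays.

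The consequence is the loss of an objective cross-check on event-based fever and CRS counts in a study with unblinded staff. The documents do not show that those counts are wrong, and no estimate, stopping decision or efficacy analysis changes. The conclusion assumes that 11.7.3 is the complete set of limits used for Table 2.21 and Listings 33 and 34. If the sponsor's standards supply a temperature range, a line in the SAP saying so and giving the range would settle that part. It is a worthwhile improvement at almost no cost, not a flaw that threatens the trial's conclusions.

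**What to change.** Make a reporting change only, leaving every stopping and clinical rule as it is.

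- Add body temperature to SAP 11.7.3, using the bands already in protocol Table 5: 38.0 to 39.0, above 39.0 to 40.0, and above 40.0 degrees C. The top band combines grades 3 and 4, which differ by duration.
- In Table 2.21, show each patient's worst post-baseline temperature category by dose, overall and separately for the dosing period. State which definition of that period applies: SAP Section 7 ends it on the day of the last dose, and SAP 11.3.1 one day later.
- State that unscheduled and 30-minute repeat readings count towards the worst case, as an explicit exception to SAP 11.4.3.
- Let Listings 33 and 34 flag temperature, so that fever-only patients appear.

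The cost is one row in 11.7.3, a short note on Table 2.21 and minor programming. The data are already collected and the bands are already in the protocol.
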